**COVER PAGE**

**STATISTICAL ANALYSIS PLAN**

**OFFICIAL TITLE: PET Imaging Study of Amish and Mennonite Patients with *CNTNAP2* Mutations**

**NCT NUMBER: NCT02983058**

**DATE OF DOCUMENT: May 22, 2019**

## Statistical Analysis Plan

The study was designed to enroll 40 individuals (20 affected with the mutation and 20 unaffected) in a cross-sectional biomarker validation study comparing PET mGluR5 binding between *CNTNAP2* mutation carriers and their unaffected first-degree relatives.

*Specific Aim 1:* Validate PET mGluR5 binding as a downstream marker of mTOR kinase hyperactivity, using individuals with *CNTNAP2* as an “experiment of nature” to assess consequences of mTOR kinase-pathway mutations on PET mGluR5 binding.

Primary hypothesis: mGluR5 binding will differ in patients with *CNTNAP2* mutations compared with normal controls.

Two-sample t-tests will be used to test for the global effects of *CNTNAP2* mutation versus unaffected controls on mGluR5 PET ligand binding, with regional  $BP_{ND}$  in DLPFC as the primary outcome variable. Two-sided statistics will be used, to assess potential increases or decreases in mGluR5 PET binding, related to underlying alterations in mGluR5 expression.

Decay-corrected reconstructed PET images will be co-registered to the anatomical MRIs acquired at the beginning of the study, using maximization of mutual information as implemented in SPM8 software. ROIs will be drawn on the MRIs and transferred to the co-registered PET images. Included ROIs will be: HPC and prefrontal (dorso-lateral, medial and orbitofrontal) cortices (19,20), as well as associative, sensorimotor, and ventral subregions of the striatum, thalamus, and occipital, parietal, and temporal cortices. In addition, cerebellum will be included as a reference region to estimate the distribution volume of the non-displaceable compartment ( $V_{ND}$ ). Time activity curves will be generated from ROI data and subsequently fitted to a 2-tissue compartment model (2TC) with arterial plasma input. Total distribution volume ( $V_T$ ) will be computed in each region including cerebellum from the estimated rate constants. The binding potential relative to the non-displaceable compartment,  $BP_{ND}$ , will be computed indirectly as  $[V_T(ROI)/V_T(CER)] - 1$ .

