## **Power Analysis**

### **Interim Futility Analysis Plan**

An interim futility analysis will be performed after 10 patients and 10 unaffected first-degree relatives participate in this study. Using the conditional power approach, we have determined the probability that a certain effect size will be found to be significant at the end of the study given the observed effect size at the interim. These probabilities were calculated using simulated data under scenarios matching our design (SAS program available upon request). Assuming a true mean standardized difference (i.e., effect size) of 0.90 between the two groups, if we observe the sample mean standardized difference is less than 0.10 in absolute value between the groups at the midterm (i.e. n=10 in each group), there would be a 23% chance of still finding a significant difference between the groups by the end of study. With an observed midterm difference between 0.10-0.20, 0.20-0.30, or 0.30-0.40 there would be a 30%, 42%, or 50% respectively chance of still detecting a significant difference at the end of study. Thus even with only small differences at the midterm, the chances of still finding a significant result by the end is non-trivial. *Therefore, a cutoff for futility would occur only if the between group effect size is <.10 at the time of mid-point analysis.* Nevertheless, other factors including feasibility and data distribution will be considered and NIMH will have unilateral authority over whether to proceed to phase 2 of the study based upon the results of the interim futility analysis. Screen fails and withdrawals prior to PET scanning will be replaced so the number of evaluable subjects will be reduced only by failure to obtain adequate PET data.

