### **Final Analysis Plan**

This sample size is justified by prior *in vivo* human studies that have found significant differences in mGluR5 PET binding with similar sample sizes: 10-23% reductions were detected between depressed patients (n=11) versus healthy (n=11), 5% reductions between sleep deprived versus non-sleep deprived periods in a within person design (n=22). These reductions translate to effect sizes (by scaling the standard errors by sample sizes) of 0.95-1.2 and 0.90. With the proposed sample size of 20 affected individuals versus 20 unaffected 1st degree relatives, with a two-sided alpha level equal to 0.05, we have >80% power to detect effect size differences of 0.90. Assuming the affected versus unaffected differences in mGluR5 PET binding are at least as large as those found due to depression or sleep, we will have >80% power to detect it. For the exploratory aim, we will be able to detect correlations of 0.35 or greater to be statistically significant with alpha = 0.05 and >80% power.

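### The power and conditional-power figures assume that every scan is evaluable, but failed PET scans are not replaced and no allowance is made for them

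*SAP*

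**What the plan says.** - **Enrolment** (SAP, opening section): "The study was designed to enroll 40 individuals (20 affected with the mutation and 20 unaffected".
- **Primary analysis** (same section): "Two-sample t-tests will be used to test for the global effects", two-sided, with DLPFC BP_ND as the primary outcome. BP_ND is derived from a two-tissue compartment fit with arterial plasma input, in both the target region and the cerebellum.
- **Power** (Final Analysis Plan): "With the proposed sample size of 20 affected individuals versus 20 unaffected" first-degree relatives, and "with a two-sided alpha level equal to 0.05", the SAP states that "we have >80% power to detect effect size differences of 0.90".
- **Interim trigger** (Interim Futility Analysis Plan): "An interim futility analysis will be performed after 10 patients and 10 unaffected first-degree relatives participate in this study". The conditional powers of 23%, 30%, 42% and 50% are given for an observed difference "between the groups at the midterm (i.e. n=10 in each group").
- **Replacement** (same section): screen fails and withdrawals before PET scanning are replaced, "so the number of evaluable subjects will be reduced only by failure to obtain adequate PET data".

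The SAP gives no PET failure rate, no replacement of failed scans and no inflated sample size.

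**The concern.** The SAP names one source of loss that it will not make good, then quotes both sets of operating characteristics as though that loss were zero. A participant contributes to the primary analysis only if the image, the arterial input and the compartment fits in DLPFC and cerebellum all succeed. If any of these fails, there is no BP_ND as the plan defines it.

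Two things are at stake. First, the power figure that justifies the sample size is a best case, and readers will take it as the expected case. Second, the interim is worded by participation, while its probabilities are computed for 10 evaluable values per group. If a scan fails in phase I, the figures used for the stop/go decision do not describe the look actually taken.

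**Working it through.** **Inputs.** From the SAP: n = 20 per group, standardized difference d = 0.90, two-sided alpha 0.05, two-sample t-test, interim at 10 per group, and futility if the observed |d| is below 0.10. Assumed, because the SAP gives no figure: PET failure rates of 5% (19 per group left) and 10% (18 per group left).

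**Step 1. Reproduce the stated power.** The noncentrality is d / √(1/n₁ + 1/n₂). At 20 per group it is 0.90 / √(2/20) = 2.846.
- Normal approximation: Φ(2.846 − 1.960) = 81.2%. This reproduces the SAP's figure, and 20 per group is the smallest n that reaches 80% by this formula.
- Noncentral t, 38 degrees of freedom, critical value 2.024: 79.2%. This matches the planned test and falls just short of 80%. Under the t-test, 21 per group gives 81.2%.

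**Step 2. Remove failed scans** (same formulas, d = 0.90).

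| Evaluable per group | Assumed failure rate | t-test | Normal approximation |
|---|---|---|---|
| 20 + 20 | 0 | 79.2% | 81.2% |
| 20 + 19 | one scan in all | 78.1% | 80.2% |
| 19 + 19 | 5% | 77.0% | 79.2% |
| 18 + 18 | 10% | 74.6% | 77.0% |

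Each scan lost in both groups costs about 2 points. One failure in each group puts power below 80% by either method.

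**Step 3. Reproduce the interim figures.** Simulation with true d = 0.90, 10 per group at the interim and 20 at the end:

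| Observed abs. d at interim | SAP | Final z test, SD known | Final t-test |
|---|---|---|---|
| below 0.10 | 23% | 24.0% | 18.6% |
| 0.10–0.20 | 30% | 29.9% | 24.9% |
| 0.20–0.30 | 42% | 39.9% | 34.4% |
| 0.30–0.40 | 50% | 50.5% | 45.1% |

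The stated figures reproduce to about 2 points with a known-SD test at full 10 and 20 per group. With 9 then 18 evaluable, the t-test figure in the lowest band falls from 18.6% to 15.2%.

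**Step 4. Effect on the futility rule.** The chance that the observed |d| is below 0.10 when the true d is 0.90 is 2.4% at 10 per group and 2.7% at 9 per group, a rise of about 0.3 points.

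**Step 5. How likely is any loss?** At an assumed 5% failure rate per scan, independent across participants, the chance of at least one failure is 1 − 0.95²⁰ = 64% among the first 20 participants and 1 − 0.95⁴⁰ = 87% among all 40.

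**The case against.** **The SAP discloses the residual loss and does not claim 20 evaluable per group after losses.** That is fair as to candour. But the disclosure is not carried into the power figure, and the figure has no margin to absorb it.

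**A reader might infer that both looks will run below their stated sizes.** The document does not support that. It gives no failure rate; with no failures both sizes are met, and failures confined to phase II would leave the interim at 10 per group.

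**A reader might also take it as settled that a failed scan counts towards the interim 10.** The word used in the Interim Futility Analysis Plan, and the replacement rule in the same section, make this the likelier reading. Elsewhere the SAP speaks of the assessment of 10 patients and 10 relatives, and it never says explicitly that a non-evaluable participant counts. The wording is loose rather than decided.

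**The interim consequence is slight.** This stands. The chance of a wrongful futility signal barely moves, the cutoff is not mechanical, and NIMH weighs other factors and would presumably see a shortfall in evaluable scans.

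**Part of the shortfall is not attrition.** This also stands. The gap from 81.2% to 79.2% at a full 20 per group comes from using a normal approximation for a t-test.

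**Power is taken at the smallest effect the SAP cites.** True: at d = 0.95, 19 per group still gives 81.3%. But 0.90 is the value to which the SAP attaches its claim, so the claim must be judged there.

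**Conclusion.** The point holds in a limited form. The power statement rests on 20 evaluable scans per group and the conditional powers on 10, while failed scans are neither replaced nor allowed for. Any failure therefore takes the evaluable number below the computed basis. For the planned two-sided t-test at d = 0.90, power is 79.2% with no failures, 77.0% at 19 per group and 74.6% at 18. The 19- and 18-per-group figures depend on failure rates assumed here, with losses equal in the two groups.

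The loss is modest, but the stated figure sits on the 80% line, so even a small loss makes it wrong. The consequence for the futility decision is minor. What needs correcting is chiefly the stated power.

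**What to change.** 1. In the Final Analysis Plan, restate the power at d = 0.90 for the planned t-test: about 79% if all 40 scans are evaluable, and about 75–77% if 5–10% are not. State the failure rate expected and its source.
2. In the Interim Futility Analysis Plan, define the trigger as 10 evaluable DLPFC BP_ND values per group. Alternatively, keep the present trigger and recompute the conditional powers at the number actually evaluable.

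The cost is SAP wording, a less favourable power statement, and possibly a short wait at the interim for scans already planned. Neither step restores power. If the sponsor wants to keep 20 evaluable per group, failed scans must be replaced or the sample inflated: 20/0.95 rounds up to 22 scans per group at a 5% failure rate, and 20/0.90 to 23 at 10%. That costs extra scans. Even then the t-test power is 79.2%; exceeding 80% takes 21 evaluable per group.

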### **Final Analysis Plan**

This sample size is justified by prior *in vivo* human studies that have found significant differences in mGluR5 PET binding with similar sample sizes: 10-23% reductions were detected between depressed patients (n=11) versus healthy (n=11), 5% reductions between sleep deprived versus non-sleep deprived periods in a within person design (n=22). These reductions translate to effect sizes (by scaling the standard errors by sample sizes) of 0.95-1.2 and 0.90. With the proposed sample size of 20 affected individuals versus 20 unaffected 1st degree relatives, with a two-sided alpha level equal to 0.05, we have >80% power to detect effect size differences of 0.90. Assuming the affected versus unaffected differences in mGluR5 PET binding are at least as large as those found due to depression or sleep, we will have >80% power to detect it. For the exploratory aim, we will be able to detect correlations of 0.35 or greater to be statistically significant with alpha = 0.05 and >80% power.

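### The planning effect size of 0.90 comes from a within-person study but is used unconverted for an unpaired 20 versus 20 t-test, so more than 80% power for a sleep-sized difference is not supported

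*SAP*

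**What the plan says.** The SAP's Final Analysis Plan justifies the sample size from two earlier PET studies. The first compared 11 depressed patients with 11 healthy people and found reductions of 10% to 23%. The second is described as "5% reductions between sleep deprived versus non-sleep deprived periods in a within person design (n=22". On how these became effect sizes, the SAP says only: "These reductions translate to effect sizes (by scaling the standard errors by sample sizes) of 0.95-1.2 and 0.90". The range 0.95 to 1.2 belongs to depression and 0.90 to sleep.

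The next sentence applies 0.90 to the present design: "With the proposed sample size of 20 affected individuals versus 20 unaffected" relatives, and "with a two-sided alpha level equal to 0.05, we have >80% power to detect effect size differences of 0.90". The conclusion is then put in terms of both studies: "Assuming the affected versus unaffected differences in mGluR5 PET binding are at least as large as those found due to depression or sleep", power will exceed 80%.

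The primary test is unpaired. Under Specific Aim 1, "Two-sample t-tests will be used to test for the global effects of" the mutation against unaffected controls. The Interim Futility Analysis Plan uses the same value for its simulations: "Assuming a true mean standardized difference (i.e., effect size) of 0.90 between the two groups".

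The SAP gives no within-person correlation, between-person SD or conversion from the paired to the unpaired scale.

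**The concern.** In a within-person study the standard error of the change normally reflects the SD of paired differences. That SD leaves out the stable variation between people. An unpaired comparison of carriers with relatives has to contend with all of that variation. When repeated measurements on the same person are strongly correlated, an effect size on the paired scale is therefore much larger than the same raw difference on the between-person scale.

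The sleep study is the only cited source of the value 0.90. If that value is on the paired scale, the SAP claims the same sensitivity to a sleep-sized difference as to a depression-sized one, and only the second claim has support. This affects how convincing the sample-size justification is and how a null result would be read. A reader could wrongly conclude that a 5% difference had been reasonably excluded.

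**Working it through.** **Inputs.** From the SAP: unpaired two-sample t-test (Specific Aim 1); 20 per group, two-sided alpha 0.05, sleep study with a 5% reduction and effect size 0.90, depression study with 10% to 23% reductions and effect sizes 0.95 to 1.2 (all Final Analysis Plan). Not in the SAP, and so varied below: the within-person correlation rho and the between-person SD.

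**Step 1. Reproduce the stated power.** For 20 per group and d = 0.90, the normal approximation gives 81.2%, which matches the stated figure of more than 80%. The exact noncentral t (38 df) gives 79.2%. Exact 80% power needs d = 0.909. The arithmetic at 0.90 is therefore sound to within the choice of approximation; the question is the scale of the input. The depression values give 83.3% (d = 0.95) and 95.9% (d = 1.2) by exact t.

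**Step 2. Convert, if 0.90 is a paired standardised difference.** With equal SDs, the SD of paired differences is SD × sqrt(2(1 − rho)), so

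d(between) = 0.90 × sqrt(2(1 − rho)).

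| rho | d(between) | Exact power, 20 vs 20 |
|---|---|---|
| 0 | 1.273 | 97.5% |
| 0.3 | 1.065 | 90.7% |
| 0.5 | 0.900 | 79.2% |
| 0.6 | 0.805 | 69.9% |
| 0.7 | 0.697 | 57.5% |
| 0.8 | 0.569 | 41.9% |
| 0.9 | 0.402 | 23.7% |

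Setting d(between) = 0.909 gives rho = 1 − 0.909²/(2 × 0.90²) = 0.49. Under this reading, 80% power holds only at a correlation of about 0.49 or less.

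**Step 3. Compare the SDs implied by the SAP's own figures.** The implied SD is the percentage reduction divided by the effect size. For sleep it is 5/0.90 = 5.6%. For depression the SAP does not say which reduction goes with which effect size, so all four pairings are shown. The last two columns assume that the depression study's SD applies here. The implied correlation also assumes that 0.90 is on the paired scale: rho = 1 − 5.56²/(2 × SD²).

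| Pairing | Implied SD | d for a 5% difference | Exact power for 5% | Implied rho |
|---|---|---|---|---|
| 10/1.2 | 8.3% | 0.600 | 45.6% | 0.78 |
| 10/0.95 | 10.5% | 0.475 | 31.0% | 0.86 |
| 23/1.2 | 19.2% | 0.261 | 12.7% | 0.96 |
| 23/0.95 | 24.2% | 0.207 | 9.8% | 0.97 |

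The like-with-like pairings are the two middle rows (31% and 13%). Every pairing gives a between-person SD larger than 5.6%, and none brings a 5% difference near 80% power.

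**Step 4. The opposite case.** If the per-condition standard error was scaled, 0.90 is already on the between-person scale and carries over, with the 79.2% of Step 1.

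**The case against.** The strongest reply is that the source study cannot be seen. The SAP does not say which standard error was scaled, so it is not established that 0.90 needed converting. Even on the paired scale the direction of error is open, since a correlation below 0.49 gives more than 80% power. This stands, and it limits the finding to not supported rather than shown to be wrong.

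The SD comparison can also be challenged. The two studies may differ in region, measure and population, the SAP does not pair reductions with effect sizes, and the ends of the 8% to 24% range come from crossing the pairs. That is fair, so the comparison is an indication and not proof. The like-with-like pairings nevertheless point the same way.

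The power sentence could also be read in standardised units, in which case it simply restates the calculation at 0.90. The wording permits that. It does not rescue the claim, because the standardised unit of a paired study need not be that of an unpaired one.

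Finally, the depression study alone gives 0.95 to 1.2, above 0.90, with 83% to 96% power, so 20 per group keeps a between-person justification. This is correct and limits the consequence. It leaves the separate claim about sleep without support.

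**Conclusion.** The concern holds. The claim of more than 80% power for a sleep-sized difference is not supported by the SAP, because the scale of 0.90 is not stated and the design it came from differs from the design it is used for.

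The size depends on unknowns. If 0.90 is a paired value, power falls from 79% at a correlation of 0.5 to 24% at 0.9. If the depression study's SDs apply, a 5% difference has 10% to 46% power, or 13% to 31% on like-with-like pairing. If per-condition standard errors were scaled, 0.90 carries over at 79%, just under the stated level by exact t. That the paired reading is the likelier one is an inference, held with medium confidence; the absence of a derivation is certain.

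The depression half of the sentence is unaffected, as are the sample size, test, alpha and futility cutoff. The point should be fixed because the sentence is part of the stated justification for the sample size.

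**What to change.** In the SAP's Final Analysis Plan, do one of two things:

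- remove the reference to sleep from the power claim; or
- say which standard error was scaled to give 0.90 and, if it was that of paired differences, convert it with a stated within-person correlation.

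In either case:

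- justify the between-group effect size from between-person data only;
- state that 20 per group gives 80% power for a standardised difference of about 0.91 (79% at 0.90 by exact t);
- label any translation into a percentage difference as dependent on the assumed between-person SD. At SDs of 8.3% to 24.2%, the detectable difference is 0.909 × SD, about 8% to 22%.

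Because the futility simulations also assume 0.90, conditional-power figures at a smaller effect size could be added, but this is optional.

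The cost is SAP wording and a less favourable statement of sensitivity. No participants are added, and the test, alpha and futility cutoff stay as they are.

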*Specific Aim 2:* Evaluate PET mGluR5 binding in other brain regions of potential relevance, including hippocampus (HIPP) and primary visual cortex (occipital pole) in order to determine ideal regions of interest for future intervention studies.

*Specific Aim 3:* Determine the interrelationship between PET mGluR5 binding across brain regions and symptoms in psychosis disorder patients.

Statistical analysis will be conducted in two phases. The first analysis (i.e., interim analyses, see Power analysis, below) will be conducted following assessment of 10 patients/10 unaffected first-degree relatives, and will provide information to determine whether or not to continue to the second phase of the study. The decision about continuing to phase II will be made by NIMH following review of the phase I data. Of note, the phase I data will be used only for futility analyses to decide on whether or not to proceed with the second study phase.

If the decision is made to proceed to phase II, a second analysis will be conducted using pooled data across the two phases to test the *a priori* hypotheses. Because of the limited sample size and our use of Phase I data solely for the purpose of futility, no statistical correction will be made for the separate analyses conducted following phase I of the study.

Secondary analyses will evaluate group differences in  $BP_{ND}$  at additional ROIs including hippocampus and visual cortex. In exploratory analyses, Pearson’s correlation coefficient (or

Spearman's rho (if data appear non-normal) will be used to investigate relationships between scores on the clinical assessments and BPND within pre-defined brain regions.

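### The claim of over 80% power for correlations of 0.35 is false: power is about 61% with all 40 participants and 34% with the 20 patients, where an observed 0.35 would not be significant

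*SAP*

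**What the plan says.** The Final Analysis Plan closes its power section with a statement for the exploratory aim: "we will be able to detect correlations of 0.35 or greater to be statistically significant with alpha = 0.05 and >80% power". It gives no sample size and no sidedness for that statement. The preceding power statement, for the group comparison, is made "with a two-sided alpha level equal to 0.05".

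The only sample size in the SAP is in its opening sentence: "The study was designed to enroll 40 individuals (20 affected with the mutation and 20 unaffected"). The analysis in question is Aim 3, which is to study the "interrelationship between PET mGluR5 binding across brain regions and symptoms in psychosis disorder patients". The method is Pearson's correlation, or Spearman's if the data look non-normal; it "will be used to investigate relationships between scores on the clinical assessments and BP"<sub>ND</sub> within pre-defined regions. The SAP does not say whether these correlations use the affected participants only or both groups.

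**The concern.** A correlation of 0.35 is moderate, and detecting one reliably usually takes more than 40 people. Here the total is 40, and the wording of Aim 3 points to patients, of whom there are 20. The power figure therefore looked too high under either reading.

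This sentence is the only operating characteristic the SAP gives for Aim 3. A reader who relies on it could take a non-significant correlation as evidence against moderate associations, although the study would miss a true 0.35 more often than the stated 20%.

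Two related points bear on which sample the claim refers to. First, Aim 3 names psychosis disorder patients, but the SAP forms its groups by *CNTNAP2* mutation status and nowhere links the two. Second, if all 40 participants were used to gain numbers, the groups may differ in both binding and symptoms. That alone creates a correlation across the pooled sample, even with no association within either group.

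**Working it through.** **Inputs from the SAP.** True correlation r = 0.35, alpha = 0.05 and claimed power above 80% (Final Analysis Plan); n = 40 in total, 20 of them affected (opening paragraph). Two-sided testing is assumed because the preceding power statement is two-sided; one-sided was also tried.

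**Attempt to reproduce the stated figure.** By Fisher's z, with the small-sample bias term,

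power = Φ( [atanh(r) + r/(2(n−1))] × √(n−3) − z₁₋α/₂ ), with atanh(0.35) = 0.3654 and z₀.₉₇₅ = 1.960.

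- n = 40: (0.3654 + 0.35/78) × √37 = 0.3699 × 6.083 = 2.250; 2.250 − 1.960 = 0.290; power = 61.4%.
- n = 20: (0.3654 + 0.35/38) × √17 = 0.3747 × 4.123 = 1.545; 1.545 − 1.960 = −0.415; power = 33.9%.

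The result does not depend on the approximation or on sidedness. The simulation applies the exact t-test of Pearson's r to bivariate normal data, 200,000 samples per case:

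| n | Sides | Fisher z, no bias term | Fisher z, bias term | Noncentral t | Simulation |
|---|---|---|---|---|---|
| 40 | two | 60.4% | 61.4% | 63.4% | 61.5% |
| 40 | one | 71.8% | 72.8% | 75.0% | 72.9% |
| 20 | two | 32.5% | 33.9% | 35.3% | 33.5% |
| 20 | one | 44.5% | 46.0% | 48.5% | 46.2% |

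The stated figure is not reproduced by any variant. The most favourable cell is 75%.

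**Would an observed 0.35 be significant?** The two-sided critical value is r = t/√(n−2+t²), with t the 97.5% point on n−2 degrees of freedom.

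- n = 40: t = 2.024; 2.024/√(38 + 4.098) = 0.312. An observed 0.35 is significant (p = 0.027).
- n = 20: t = 2.101; 2.101/√(18 + 4.414) = 0.444. An observed 0.35 is not significant (p = 0.13). The one-sided critical value, 0.378, also exceeds 0.35.

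**Sample needed for 80% power at 0.35.** n = ((1.960 + 0.842)/0.3654)² + 3 = 61.8, so 62 without the bias term. With the bias term, 61 suffices (79.4% at 60, 80.1% at 61).

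**Correlation detectable with 80% power.** Without the bias term, r = tanh(2.802/√(n−3)): 0.431 at n = 40 and 0.591 at n = 20. With the bias term: 0.426 and 0.581. A partial correlation adjusted for group costs one degree of freedom, so 40 people behave as 39 would: 0.431 with the bias term, and 80.0% simulated power at 0.43. The rounded figures are therefore 0.43 for all 40 (adjusted or not) and 0.58 for the 20 affected.

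**Pooling artefact.** With two equal groups and no within-group correlation, the pooled correlation is the product of two terms of the form d/√(d²+4), one for each variable's standardised group difference. For binding, the SAP's own effect size d = 0.90 gives 0.90/√(0.81 + 4) = 0.410. The SAP gives no group difference for the clinical scores, so 1, 2 and 3 SD are assumed:

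- 1 SD: 0.410 × 0.447 = 0.18
- 2 SD: 0.410 × 0.707 = 0.29
- 3 SD: 0.410 × 0.832 = 0.34

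The last value is close to the 0.35 that the plan sets out to detect.

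**The case against.** The arithmetic cannot be rebutted; the case on the other side is about weight and scope.

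- **The aim is exploratory.** The correlation figure does not set the sample size, which rests on the group effect of 0.90. It does not enter the futility rule or the primary test in DLPFC. This stands and limits the consequence, but the plan chose to state a numerical guarantee, and the guarantee is wrong.
- **No n is given for the sentence.** At n = 40 an observed 0.35 would be significant, so the significance half of the claim would be true. That also stands. But the sentence promises "alpha = 0.05 and >80% power" as well, and that half fails at both 40 and 20.
- **The SAP never says the groups will be pooled for the correlations.** Where it speaks of pooled data, it means pooling across the two study phases. This is fair: the artefact is conditional, and the symptom differences used to size it are assumed. It remains relevant because the SAP does not exclude pooling, and pooling is the only route to n = 40.
- **The affected participants may have psychosis diagnoses.** Eligibility belongs to the protocol, which is not at hand, so this cannot be excluded. Within the SAP, however, Aim 3's label does not match groups defined by mutation status, and this leaves the analysed sample unclear.
- **The SAP states no rule for interpreting a null correlation.** True. The risk of misreading one is a judgement about how power statements are used.

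**Conclusion.** The concern holds. At a true correlation of 0.35 and two-sided alpha 0.05, power is about 61% with all 40 participants and about 34% with the 20 affected. The shortfall from the stated 80% is at least 19 points on the first reading and 46 on the second. The study would miss such a correlation about 39% or 66% of the time, against at most 20% as claimed. On the patient-only reading, an observed 0.35 would not be significant either.

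These figures assume bivariate normal data, Pearson's test, complete evaluable data and no adjustment for testing several regions and scores. Scans lost to inadequate PET data, or a multiplicity adjustment, would lower power further. The conclusion does not depend on the unstated sample or sidedness, since no combination reaches 80%. The pooling illustration rests on assumed symptom differences, and the power error stands without it. The primary analysis is not affected.

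**What to change.** 1. Replace the closing sentence of the Final Analysis Plan with: *With 20 affected participants there is 80% power for |r| of at least 0.58; across all 40, adjusted for group, for |r| of at least 0.43 (two-sided alpha 0.05).*
2. State that symptom correlations will be run in the affected participants, or as partial correlations adjusted for group if both groups are used, so that a group contrast is not reported as an association.
3. In Aim 3, replace the reference to psychosis disorder patients with the population actually enrolled and analysed.

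The cost is SAP wording only, with no change to enrolment, procedures or the primary analysis. The stated detectable correlation becomes less favourable, which is what the design supports.
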